### **6.2 Age matched control group**

#### **6.2.1 Inclusion criteria**

- Children aged between 8 to 18 years of age

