## 2 RATIONALE

Mechanisms of shoulder instability, and the subsequent development of arthritis, are poorly understood (Deitch, Mehlman et al. 2003, McFarland, Kim et al. 2003, Barden, Balyk et al. 2005, Barrett 2015). Both surgical and nonsurgical interventions are based on a current understanding of the associated mechanisms that may include anatomical predisposition (shallow glenoid, lax ligament and capsule), weak muscles, or inappropriate muscle coordination (Harryman, Sidles et al. 1992, Cordasco 2000, Inui, Sugamoto et al. 2002, Deitch, Mehlman et al. 2003, McFarland, Kim et al. 2003, Barden, Balyk et al. 2005, Hovelius and Saeboe 2009, Jaggi and Lambert 2010, Jaggi, Noorani et al. 2012, Barrett 2015, Longo, van der Linde et al. 2016, Bateman, Jaiswal et al. 2018, Best and Tanaka 2018).

Rehabilitation approaches are preferred over surgical methods for the growing child, and management is therefore aimed at addressing predominant factors associated with these mechanisms e.g. exercises to improve co-ordination of the shoulder muscles if the source of instability is dysfunctional muscle control. However, failure rates are high (approximately 70% - 90%), indicating that current understanding of these mechanisms is limited.

In children, this can have detrimental long-term effects. This research is important as shoulder instability, mainly subluxation and dislocation, is common (23.9/100,000 person years but can be as high as 164.4 for 14 -16 year olds) (Leroux, Ogilvie-Harris et al. 2015) resulting in pain, decreased movement and functional limitations. Diagnosis of shoulder instability is normally delayed (on average by 2-years) and 70% of children have repeated dislocations (Longo, van der Linde et al. 2016), often associated with premature glenohumeral arthropathy (odds ratio 19.3) (Marx, McCarty et al. 2002, Deitch, Mehlman et al. 2003).

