#### **4 STUDY DESIGN**

This is an observational, cross-sectional study of children (aged 8 to 18) presenting with shoulder instability of any origin, traumatic or atraumatic (n=15) and an age-matched sample (n=15) with no history of shoulder problems. Muscle activity and movement pattern differences will be measured using non-invasive 3D motion capture and surface electromyography, to identify factors responsible for instability. Only a single visit to the site will be required (ORLAU, RJAH). No interventions or treatments are included in this study as this is an observational, cross-sectional study.

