## **7 STUDY PROCEDURES**

### **7.1 Recruitment**

Our main recruitment site is based at RJAH outpatient clinics, Shropshire. Potential participants on their routine hospital visits, who fit the inclusion/exclusion criteria, will be given brief information about the study by their treating physician/surgeon/therapist. The study will additionally be advertised in clinical centres in the West Midlands such as specialist clinics, GP services and primary care settings, where practitioners will signpost potential participants to the primary organisation. If potential participants express an interest in the study the treating physician/surgeon/therapist may also pass on the relevant contact details to the study team. Posters with information regarding the study will also be located in the respective departments. We will also advertise the study and raise awareness of the study through social media using an electronic version of the poster advertisement.

Children without shoulder instability will be recruited by contacting staff within the hospital using the RJAH staff mailing list using the email included with this submission.

Investigation of referral patterns with clinical collaborators (ORLAU, RJAH, Oswestry) demonstrates that clinical recruitment is realistic and achievable. There are approximately 2 referrals a month for children with instability who meet our inclusion criteria.

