### 7.1.3 Screening for age matched controls

All screening questions must have a positive response to be eligible for the study

	CRITERIA	YES	NO	CHECK
1.	Aged between 8 to 18 years			
2.	NO previous presentation to a health care professional with a diagnosis of shoulder instability			
4.	NO history of shoulder injury within the last 3 months on the arm being assessed			
5.	NO co-existing neurological pathologies or deficits			
6.	NO previous surgical intervention on the arm being assessed			
7.	NOT currently undergoing or awaiting medical management, diagnostic investigations or rehabilitation on the arm being assessed			

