## 8 STATISTICS AND DATA ANALYSIS

### 8.1 Sample size calculation

This is an observational, cross-sectional study.

- A power calculation, used to determine the required sample size, is not possible for this study as the standard error of measurement (SEM - essential to identify a minimally clinically important difference) is not known.
- This study will provide the data from which SEM can be estimated and this can then be used to inform power calculations for future studies.
- Our rationale for selecting a sample size of 15 in each group (30 total) has been based on previous work which has developed and then implemented protocols for clinical practice.
- The two references cited below have developed clinical measurement protocols using sample sizes of 10 typically developing children and 12 children with cerebral palsy affecting the upper limbs.
- In the absence of an equivalent study in paediatric shoulder instability a sample size of 15/group reflects the current research practice in the literature and will be able to provide us with population estimates of “standard error of measurement - SEM” in typically developing children and those with upper limb pathology.

Jaspers, E., et al., Upper limb kinematics: development and reliability of a clinical protocol for children. *Gait Posture*, 2011. 33(2): p. 279-85.

Jaspers, E., et al., The reliability of upper limb kinematics in children with hemiplegic cerebral palsy. *Gait & Posture*, 2011. 33(4): p. 568-575.

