  - i) data from study objective 2 will be evaluated to identify features i.e. movement or muscle activity patterns, which may be used to categorise clinical presentations of shoulder instability. An appropriate clustering/categorisation method will be selected once the characteristics of the dataset has been established

if we get a large enough sample size of participants with a homogenous clinical presentation and if three or more groups are identified in the preceding work package, an analysis of variance (ANOVA) can be used. For less than three groups, an independent sample t-test will be used.

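### Controls are called age-matched, but no matching rule is stated and no planned comparison uses age or sex, so an imbalance could be read as a feature of instability

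*Combined protocol and SAP*

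**What the plan says.** Section 4 promises "an age-matched sample (n=15) with no history of shoulder problems", and the Study Summary uses the same label. Section 6.2, headed as the age-matched control group, has one inclusion criterion: "Children aged between 8 to 18 years of age". Section 6.1.1 sets the same range for cases. The control checklist in 7.1.3 states that "All screening questions must have a positive response to be eligible for the study", but its age item asks only whether the child is within 8 to 18. No age window, pairing, frequency table or sex rule appears in the text.

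The two groups come from different sources. Cases come mainly from outpatient clinics and referrals. For controls, 7.1 says "Children without shoulder instability will be recruited by contacting staff within the hospital using the RJAH staff mailing list".

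In 8.3 the group comparison is descriptive: means and SDs for kinematics, and descriptive statistics for force and strength. A formal test appears only under objective 3. It depends on a large enough homogeneous sample and on the groups found in the preceding categorisation step. ANOVA can be used for three or more groups; otherwise, "For less than three groups, an independent sample t-test will be used". No covariate and no matched analysis is named.

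**The concern.** An 8-year-old and an 18-year-old differ greatly in size and strength. The aim is to identify factors responsible for recurrent instability, so any difference between groups is a candidate factor. As written, a control group several years younger than the cases would satisfy every eligibility rule, and nothing in 8.3 would show or correct it. If the ages are in fact matched, the analysis makes no use of it, and the precision that matching could give is lost.

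Exposure differs by outcome. It is greatest where no scaling to age or body size is stated: grip strength (7.7.1), displacement and speed, and movements with a self-selected weight (7.7.4). It is smaller for sEMG onset timing and for activity expressed as a percentage of maximum contraction.

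**Working it through.** There is no plan figure to reproduce. Section 8.1 says "A power calculation, used to determine the required sample size, is not possible for this study" and gives no alpha, SD or effect size.

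**Inputs from the documents:** 15 children per group; age range 8 to 18.

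**Assumptions not in the documents:** two-sided 5% level; ages uniform over 8-18, so age SD = 10/√12 = 2.89 years; age explaining R² = 0.09, 0.20, 0.40 or 0.60 of an outcome's within-group variance; equal within-group SDs; no true group effect.

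**1. Chance imbalance if both groups fill the band at random.** SE of the mean age difference = 2.89 × √(2/15) = 1.05 years. P(|difference| > 1 year) = 2 × [1 − Φ(1/1.05)] = 0.34. This gap is random, so across repeated studies it costs precision and does not inflate the error rate.

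**2. Systematic 2-year gap in mean age.** This is a separate scenario from step 1.
- Bias in SD units = √R² × 2/2.89.
- False-positive rate = two-sided rejection probability of a noncentral t with 28 df and noncentrality bias/√(2/15), where √(2/15) = 0.365.

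**3. Precision.** The ratio of unadjusted to age-adjusted SE is 1/√(1−R²) when ages balance. With a 2-year gap the adjusted variance is multiplied by 1 + [4/(28 × 8.33)]/(2/15) = 1.129, so the ratio is divided by √1.129 = 1.062.

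| R² | Bias, 2-year gap (SD) | False-positive rate, unadjusted | SE ratio, balanced | SE ratio, 2-year gap |
|---|---|---|---|---|
| 0.09 | 0.21 | 8.5% | 1.05 | 0.99 |
| 0.20 | 0.31 | 13% | 1.12 | 1.05 |
| 0.40 | 0.44 | 21% | 1.29 | 1.22 |
| 0.60 | 0.54 | 29% | 1.58 | 1.49 |

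**4. Simulation (20,000 runs, age-outcome correlation r = 0.3, 0.5, 0.7).**
- 2-year gap: the unadjusted t-test rejects in 8.5%, 14.6% and 24.7% of runs; adjustment for age holds about 5%. The 95% CI half-width is 0.77, 0.70 and 0.57 SD adjusted, against 0.74 SD unadjusted. At r = 0.3 the adjusted interval is therefore slightly wider.
- Controls matched within half a year, analysed as independent groups: the error rate is 4.2%, 2.4% and 0.8%. That is valid but conservative.

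**The case against.** - **The t-test is not clearly a case-control test.** This stands. In 8.3 it is conditional and attached to groups derived by clustering, so a reader might wrongly infer that a 15 v 15 t-test with an inflated error rate is planned. The percentages above show how misleading an unadjusted comparison could be; they are not operating characteristics of a planned test. The descriptive comparison is equally unadjusted, so the point survives.
- **Matching is a sampling step and may be specified elsewhere**, for instance in the recruitment email, which is not reproduced in the text. This is possible. The documents do not show that matching will be neglected, only that no rule is written down.
- **The cases' age distribution is unknown.** Section 2 gives an incidence of 23.9 per 100,000 person-years that "can be as high as 164.4 for 14 -16 year olds". It is tempting to infer that cases will cluster at those ages. But the reference list describes that source as covering primary anterior dislocation at ages 10 to 16, while this study also takes atraumatic, multidirectional and recurrent cases aged 8 to 18. The figure makes an imbalance plausible and no more.
- **Not every outcome tracks age.** This stands: nothing in the documents supports treating sEMG timing or normalised amplitude as largely growth-driven. Grip is measured on both arms, which allows a within-child contrast, although 8.3 does not plan one.
- **There is no primary outcome, alpha or power calculation**, so an error-rate framing is loose. That is fair, but bias in a descriptive difference does not depend on testing.

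**Conclusion.** The concern holds in a limited form. The age-matched label is not put into operation, and neither the descriptive comparison nor the conditional test uses age, sex or pairing. A growth difference could therefore be reported as a feature of instability, chiefly for unscaled strength, displacement, speed and loaded movement.

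Under the stated assumptions, a 2-year gap biases a 15 v 15 difference by 0.21-0.54 SD and takes an unadjusted 5% test to about 8.5-29%. With no systematic gap there is no bias, and the unadjusted SE is 1.05-1.58 times the adjusted one. The largest bias and the largest precision gain do not occur together: under a 2-year gap the SE ratio is about 0.99-1.49. Every figure rests on an assumed age SD, age-outcome relation and age gap. The documents do not support saying that the groups will differ in age, or that all outcome differences would be growth effects.

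**What to change.** - **Data.** Record exact age and sex for every child. It should not be assumed that age is already captured: the screening forms in 7.1.2 and 7.1.3 show only a yes/no item for 8 to 18. Tabulate both by group.
- **Section 8.3, cases v controls.** For continuous outcomes, report the difference from a linear model with group, age and sex, with a 95% CI, alongside the descriptive statistics.
- **Section 8.3, derived subgroups.** Within roughly 15 cases, adjust for age at most and label the result exploratory.
- **Section 6.2.1.** State how matching is done (for example a frequency match or an age window), or drop the term age-matched.

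**Cost.** Two data items, some wording, and two degrees of freedom in the 30-child comparison (28 to 26; t critical value 2.048 to 2.056). The interval may be slightly wider where age is only weakly related to the outcome. If matching is enforced, control recruitment through the staff list is constrained, since controls must fit the ages of enrolled cases. The modelling change can be made without that.

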#### **6.2.2 Exclusion criteria**

- Any previous presentation to a health care professional with a diagnosis of shoulder instability
- Children with a previous shoulder injury within the last 3 months on the arm being assessed that has not resolved
- Children with co-existing neurological pathologies or deficits
- Children who have had a previous surgical intervention on the arm being assessed
- Children currently undergoing or awaiting medical management, diagnostic investigations or rehabilitation on the arm being assessed

## **7 STUDY PROCEDURES**

### **7.1 Recruitment**

Our main recruitment site is based at RJAH outpatient clinics, Shropshire. Potential participants on their routine hospital visits, who fit the inclusion/exclusion criteria, will be given brief information about the study by their treating physician/surgeon/therapist. The study will additionally be advertised in clinical centres in the West Midlands such as specialist clinics, GP services and primary care settings, where practitioners will signpost potential participants to the primary organisation. If potential participants express an interest in the study the treating physician/surgeon/therapist may also pass on the relevant contact details to the study team. Posters with information regarding the study will also be located in the respective departments. We will also advertise the study and raise awareness of the study through social media using an electronic version of the poster advertisement.

Children without shoulder instability will be recruited by contacting staff within the hospital using the RJAH staff mailing list using the email included with this submission.

Investigation of referral patterns with clinical collaborators (ORLAU, RJAH, Oswestry) demonstrates that clinical recruitment is realistic and achievable. There are approximately 2 referrals a month for children with instability who meet our inclusion criteria.

#### **7.1.1 Patient identification**

Potential participants who meet the inclusion/exclusion criteria will be signposted to our study by their treating clinician or through our poster during their routine hospital visit.

### 7.1.2 Screening for children with shoulder instability

Area's in highlighted in grey must have a positive response to be eligible for the study.

	CRITERIA	YES	NO	CHECK
1.	A minimum of 12 weeks since last shoulder instability episode			
2.	Aged between 8 to 18 years			
3.	3a. Initial episode of shoulder instability OR			
	3b. Recurrent episode of shoulder instability			
4.	Subjective report of instability			*
5.	Symptomatic instability in at least one direction , confirmed by a positive clinical finding of  - Apprehension - Guarding - Laxity	5a. Sulcus (inferior)		
		5b. Anterior shift load		
		5c. Posterior shift load		
		5d. Apprehension relocation		
6.	Currently undergoing rehabilitation			
7.	Shoulder instability episode following surgical management of shoulder instability			
8.	No co-existing neurological pathologies or additional musculoskeletal injuries to the upper limb being assessed			

\*if yes must have a positive response to question 5.

### 7.1.3 Screening for age matched controls

All screening questions must have a positive response to be eligible for the study

	CRITERIA	YES	NO	CHECK
1.	Aged between 8 to 18 years			
2.	NO previous presentation to a health care professional with a diagnosis of shoulder instability			
4.	NO history of shoulder injury within the last 3 months on the arm being assessed			
5.	NO co-existing neurological pathologies or deficits			
6.	NO previous surgical intervention on the arm being assessed			
7.	NOT currently undergoing or awaiting medical management, diagnostic investigations or rehabilitation on the arm being assessed			

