## **6 ELIGIBILITY CRITERIA**

### **6.1 Children with shoulder instability**

#### **6.1.1 Inclusion criteria**

- Children aged between 8 to 18 years of age
- Subjective reports of instability with additionally symptomatic instability in the clinical assessment criteria below
- Symptomatic instability on clinical assessment in at least one direction, confirmed by a positive clinical finding (apprehension, guarding, laxity) during the sulcus, apprehension or anterior and posterior shift load tests.
- All forms of instability including multidirectional instability, atraumatic and traumatic subluxations and dislocations.
- Children presenting with an initial or recurrent episode of instability
- Children undergoing current management or rehabilitation for their shoulder at the time of the study
- Patients with surgically managed shoulder instability who have since had a further episode of shoulder instability.

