### 7.1.4 Shoulder stability tests for age matched controls (not for screening)

	CRITERIA	YES	NO	Type e.g. (L)
1.	Please make note of any clinical findings of - Apprehension (A) - Guarding (G) - Laxity (L)	1a. Sulcus (inferior) 1b. Anterior shift load 1c. Posterior shift load 1d. Apprehension relocation		

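### The control criteria do not enforce the problem-free shoulder history that the design describes, and the stability tests done on controls have no planned use

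*Combined protocol and SAP*

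**What the plan says.** Sections 1 and 4 set 15 children with instability beside 15 age-matched controls, who are said to have had no shoulder trouble in the past.

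The control criteria are in 6.2.2 and, as a checklist, in 7.1.3. The one item about instability rules out a "previous presentation to a health care professional with a diagnosis of shoulder instability". Three other items concern the shoulder or arm:
- Recent injury. Section 6.2.2 excludes "Children with a previous shoulder injury within the last 3 months on the arm being assessed that has not resolved". The 7.1.3 checklist asks about any shoulder injury in that period, resolved or not.
- Previous surgery on the assessed arm.
- Being "currently undergoing or awaiting medical management, diagnostic investigations or rehabilitation on the arm being assessed".

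Cases are defined differently. Section 7.1.2 item 4 asks for a "Subjective report of instability", and 6.1.1 requires symptomatic instability "confirmed by a positive clinical finding (apprehension, guarding, laxity) during the sulcus, apprehension or anterior and posterior shift load tests". The control checklist has no counterpart to item 4.

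Controls do undergo the same four tests, under the heading "Shoulder stability tests for age matched controls (not for screening"). Section 8.3 does not mention the results. Section 7.8 follows both groups monthly for up to 12 months for instability episodes.

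On delay, section 2 states: "Diagnosis of shoulder instability is normally delayed (on average by 2-years"). It gives the incidence as "23.9/100,000 person years but can be as high as 164.4 for 14 -16 year olds".

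**The concern.** A criterion that depends on a diagnosis is weak for a condition that the plan itself says is diagnosed late. A child whose shoulder partly slipped out six months ago, who told no clinician and has no work-up pending, passes every item in 7.1.3. If that child also has a positive apprehension test, the case definition may be met, yet the child is summarised as normal.

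With 15 per group, one child carries weight. Section 8.3 reports group means, standard deviations and absolute extremes. Section 8.1 intends the control data to supply measurement-error estimates for typically developing children, for use in later power calculations. Section 9.4 makes the dataset openly available, so a misclassified control could carry into later work. The stability tests that could help to show the problem are already being done, but nothing says what will happen to the results.

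**Working it through.** **1. Do the criteria match the description?** This needs no arithmetic. Take a child with instability symptoms, no diagnosis, no shoulder injury in the last 3 months, no surgery, and no current or awaited care. The child is outside the group described in sections 1 and 4, but passes all items in 6.2.2 and 7.1.3. The awaited-investigation item removes only children who have already sought care, so it covers part of the delay and not all of it.

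**2. How many such children, on the plan's own figures?** The plan states no such figure, so there is none to reproduce. Inputs from section 2 are an incidence of 23.9 to 164.4 per 100,000 person-years and a mean delay of 2 years. Approximate the prevalence of undiagnosed instability as incidence × delay, and give no credit for the other exclusions:
- Low: 23.9/100,000 × 2 = 0.048%. Expected among 15: 15 × 0.000478 = 0.007. Chance of at least one: 1 − (1 − 0.000478)^15 = 0.7%.
- High: 164.4/100,000 × 2 = 0.33%. Expected: 15 × 0.003288 = 0.049. Chance of at least one: 1 − (1 − 0.003288)^15 = 4.8%.

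This is probably too low. The title of the cited incidence source in section 12 limits it to primary anterior dislocation at ages 10 to 16. Cases here also include subluxation, atraumatic and multidirectional instability (6.1.1).

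**3. Range under assumed prevalence.** The documents give no prevalence covering all these forms, so the values below are assumptions. The chance of at least one is 1 − (1 − p)^15.

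| Assumed p | Expected among 15 | Chance of at least one |
|---|---|---|
| 1% | 0.15 | 14% |
| 2% | 0.30 | 26% |
| 5% | 0.75 | 54% |
| 10% | 1.50 | 79% |

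**4. Effect on a mean difference.** Let k of 15 controls have the case mean μ1 and the rest the stable mean μ0. The control mean becomes μ0 + (k/15)(μ1 − μ0), so the observed difference is (1 − k/15)(μ1 − μ0). The loss is 1/15 = 6.7% for one child, 2/15 = 13.3% for two and 3/15 = 20% for three.

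The plan sets no alpha, power or effect size. As illustration only, assume a two-sided t-test at 0.05 with 15 per group and an unchanged standard deviation. A true difference of 1.06 SD has 80% power with k = 0, and about 74%, 68% and 61% with k = 1, 2 and 3.

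**5. Effect on other summaries.** The k/15 formula does not apply to minima, maxima or standard deviations. A single child can set a group extreme.

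**The case against.** The strongest reply is that the risk is small and partly covered. The recent-injury, surgery and awaited-care items remove many symptomatic children, and the plan's own rates give under 0.05 expected children. Both points stand. It would be wrong to infer that a diagnosis is the only shoulder-related bar to entry, or that unstable shoulders are known to be in the control group. A figure such as 5% has no source in the documents and is about 15 times the highest prevalence implied by section 2 (5/0.33), so it should not be quoted without the range.

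A reader might also infer that every case-control contrast is biased towards zero. The documents do not support that. The dilution formula covers means only, and only if an untreated, undiagnosed control resembles the average enrolled case. The study names no primary outcome, its group reporting is descriptive, and the t-test or ANOVA in 8.3 is conditional on groups that have yet to be identified. The marker-perturbation work is not a group contrast.

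Nor do the documents support dropping controls on a positive test alone. Cases also need a subjective report, and laxity by itself counts as a finding, so stable but lax children would be lost. An episode during follow-up may be a new event. Omitting controls for it would select on a later outcome.

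Finally, section 7.4 takes an instability history from eligible participants without saying whether controls are included, so it is unsettled whether that history goes uncollected in controls. If it is collected, that happens after eligibility and 8.3 assigns it no use. The reply therefore reduces the size of the problem but does not remove the mismatch.

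**Conclusion.** The point holds as a gap between the design and the criteria meant to deliver it. That part rests on the text alone. How often it would matter is uncertain: 0.7% to 4.8% for at least one such control on the plan's own figures, and 14% to 79% across assumed prevalences of 1% to 10%. If one occurs and resembles the cases, a mean difference shrinks by about 6.7%, and a reported control extreme may be affected. It might be inferred that recruiting through the staff mailing list (7.1) raises the risk. The documents do not show this, since staff children could equally be diagnosed sooner, and the point does not depend on it. The change is worth making because it is nearly free and lets the control group be shown to be what sections 1 and 4 say it is.

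**What to change.** **Sections 6.2.2 and 7.1.3.** Exclude controls with a subjective report of past or current instability, using the question already put to cases in 7.1.2 item 4. Reconcile the two recent-injury wordings, one limited to unresolved injury and the other not.

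**Section 7.4.** State whether controls answer the instability history.

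**Section 8.3.** Report the control findings from 7.1.4 descriptively, by test and type of finding. Pre-specify one sensitivity analysis of the case-versus-control descriptive summaries that omits any control found to have both a reported instability history dating from before the measurement session and a positive 7.1.4 test. After the entry question is added, this would catch histories that surface later. State that laxity alone, a positive test alone, or a new episode during follow-up is not a reason for omission.

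**Cost.** One screening question, one table and one re-analysis, mostly of data already being collected. The pool of eligible controls may be slightly smaller.
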